2.2 DETAILED DESCRIPTION OF STUDY DESIGN

Study Visits and Procedures:

Timepoint	Task
Pre-Enrollment	Screening for inclusion and exclusion criteria
Before Administration of Study Drug, 0h	PCAS MD Baseline, Baseline lab data, ECHO and LSCI
During Study Drug Administration, 0h-13h	Vitals, Labs, ECHO, LSCI
Retrospective Baseline Data	Demographics, OHCA data, Clinical Lab data
Day 1 Post ROSC	VS, Labs, Clinical Lab data, PCAS MD Daily data, Interventions, Medications, SOFA
Day 2 Post ROSC	VS, Labs, Clinical Lab data, PCAS MD Daily data, Interventions, Medications, SOFA
Day 3 Post ROSC	VS, Labs, Clinical Lab data, PCAS MD Daily data, Interventions, Medications, SOFA
Discharge	Survival, CPC, mRS, CPC-E, Barthel ADL, NYHA Class, Location
30d Follow Up	Survival, CPC, mRS, CPC-E, Barthel ADL, NYHA Class, Location
90d Follow Up	Survival, CPC, mRS, CPC-E, Barthel ADL, NYHA Class, Location

****Please note that the 0h ECHO and LSCI may be collected up to one hour after the administration of the study drug to avoid issues with timing of enrollment.**

The majority of data, including all clinical lab data, that is collected for this study will be gathered during a single hospitalization. All labs will be collected within 30 minutes of their assigned time.

Follow-up data that will be obtained will not require a subsequent visit, but rather just a phone call.

Most of the baseline data elements can be effectively gathered retrospectively and will not be needed prior to starting the study drug. A small number of data elements will indeed need to be captured before study drug is administered but these can be done fairly rapidly to preclude delays in therapy onset. The same is true for data elements in days 1-3 post-arrest (0-24 h after ROSC is considered day 1)

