Research labs will be obtained by a study coordinator within 30 minutes of the assigned draw time. Labs will be run either within the UPMC Clinical Labs or the research labs of Drs. [name] or [name] as specified. We will also be collecting a small blood sample for an ancillary biomarker study for those subjects wishing to participate.

The final data to be collected will be the 90 d or discharge outcomes (whichever is later). Information that cannot be obtained by record review will be obtained either in person, or via a phone call by a member of the study team.

TABLE 1

Vital signs	Time from study drug start (hours)							
	0	3	6	9	12	24	48	72
Temperature	X	X	X	X	X	X	X	X
Heart Rate	X	X	X	X	X	X	X	X
Systolic Blood Pressure	X	X	X	X	X	X	X	X
Diastolic Blood Pressure	X	X	X	X	X	X	X	X
Mean Arterial Pressure	X	X	X	X	X	X	X	X
Arterial SBP	X	X	X	X	X	X	X	X
Arterial DBP	X	X	X	X	X	X	X	X
Arterial MAP	X	X	X	X	X	X	X	X
Pulmonary artery systolic pressure	X	X	X	X	X	X	X	X
Pulmonary artery diastolic pressure	X	X	X	X	X	X	X	X
Pulmonary artery mean pressure	X	X	X	X	X	X	X	X
Central venous pressure	X	X	X	X	X	X	X	X
Cardiac output	X	X	X	X	X	X	X	X
Vasopressors	X	X	X	X	X	X	X	X
Inotropes	X	X	X	X	X	X	X	X
Sedation	X	X	X	X	X	X	X	X
Neuromuscular blockade	X	X	X	X	X	X	X	X
Time from study drug start (hours)								
Labs (highlight represents UPMC Labs)	0	3	6	9	12	24	48	72
Troponin	X		X		X			
Arterial blood gas (ABG)	X		X		X			
Lactate	X		X		X			
Methemoglobin			X					
Neuron specific enolase (NSE)	X					X		
Plasma NO metabolites	X	X	X	X	X	X	X	X
Platelet mitochondria	X				X			
Ascorbate	X	X			X	X		
Cardiolipin	X	X			X	X		
Inflammation (integrin $\alpha 9\beta 1$ and CD11b)	X					X	X	X
Banked plasma	X	X	X	X	X	X	X	X
DNA for pharmacogenomics	X							
Whole blood pellet	X	X	X	X	X	X	X	X
Urine for renal failure markers and NO ₂ -cLA	X				X	X		
*DNA will be collected with the first scheduled blood draw after obtaining informed consent								

Outcomes

The following will be recorded at DC (+/- 3 days), and for follow up at day 30 (+/- 3 days) and day 90 (+/- 3 days) after OHCA:

*Survival

Cause of death

date/time of death

*CPC
*mRS
CPC-E
Barthel ADL
*NYHA Class
*Location of residence

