2.4 STUDY ENDPOINTS

Primary

Composite of in-hospital death, unfavorable discharge location, NYHA class III/IV heart failure at the time of discharge*

*In the setting of pre-existing heart failure or prior residence in an unfavorable location there must be at least a 1 class decrement (eg NYHA III -> IV)

Secondary

Functional

- Survival to hospital discharge, 30 and 90 days after initial OHCA
- Favorable cerebral performance category (CPC) defined as 1 or 2 at discharge, 30 and 90 days after initial OHCA
- Favorable modified Rankin score (mRS) defined as 0-3 at discharge, 30 and 90 days after initial OHCA
- Favorable discharge destination or location of residence (30 and 90 days after OHCA) defined as home or acute inpatient rehabilitation
- CPC-E at hospital discharge, 30 and 90 days after initial OHCA
- Barthel Index of Independence in Activities of Daily Living (ADL) at discharge, 30 and 90 days after OHCA

Neurologic

- Estimated likelihood of good neurologic outcome (0-100%) assessed by an experienced (>3y) member of the PCAS team blinded to treatment assignment on day 3-5 post-ROSC.
- Development of malignant EEG during hospitalization

- Time (in hours) to awakening from ROSC; defined as following commands (all values > 96h assigned 100)
- FOUR Motor + Brainstem scores on days 1-3 (requires 30 min off sedation; exclude endpoint if not medically permitted to pause sedation or paralysis)
- Presence or absence of upper and lower extremity somatosensory evoked potential N20 on comatose patients obtained any time after post-arrest day 1.
- Absolute value 24h after ROSC and change in value (24h vs 0h) of neuron specific enolase (NSE)
- EEG burst suppression ratio and change in suppression ratio
- EEG presence of dominant continuous background and reactivity to photic or tactile stimulation.

Cardiovascular

- Heart rate and mean arterial pressure (preferably off the arterial line) at 0-12 (hourly), 24h of study drug
- Persistent need for vasopressors in the first 24h after ROSC; defined as any use of norepinephrine, epinephrine, phenylephrine, dopamine or vasopressin for ≥ 3 h after study drug is initiated
- Persistent need of inotropes in the first 24h after ROSC; defined as any use of epinephrine, dobutamine, milrinone or isoproterenol for ≥ 3 h after study drug is initiated.
- ECHO measures (absolute values at end of therapy (12h) and change in 12h vs 0h):
 - tricuspid valve regurgitant velocity (TRV)

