2.5.2 Study Conduct Analysis

Continuous data will be summarized and compared using t-tests or a non-parametric equivalent should the normality assumption appear tenuous. Generalized linear mixed models, which account for non-independence of repeated assessments and endpoint structure, will be used to compare between iNO and placebo groups at multiple times. Analysis of the composite endpoint will be ascertained using an unadjusted two sample test of proportions with a type II error rate of 5%. In the event of imbalance of potential confounders after randomization an adjusted analysis will be performed using logistic regression with those unbalanced variables and treatment as the main effect of interest. Other secondary dichotomous outcomes will be summarized and compared by chi squared tests and appropriate exact methods should sample sizes be small. Time to event endpoints will be summarized by Kaplan Meir curves and compared using log rank tests. All tests will be two tailed with unadjusted $p < 0.05$ considered significant and performed using SAS 9.4.

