2.5.5 Handling Missing Data

Since our primary endpoint is ascertained at hospital discharge we expect no missing data though all analyses will be performed assuming a missing at random mechanism. No data imputation will be performed though standard sensitivity analyses, using standard missing data techniques may be used.

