5.2 INFORMED CONSENT PROCEDURES

Since the study population is comatose (part of inclusion criteria), their surrogates are often difficult to locate or emotionally not able to provide consent and the therapy must be provided rapidly, recruitment will be done under EFIC. Subjects will be enrolled if they meet the eligibility criteria unless they have opted out of the study previously. Surrogates (the legally authorized healthcare representative [LAR]) will be informed that subject is enrolled in a trial at an appropriate time, based on the judgement of the study team, by either study coordinator or PCAS MD. If family chooses to withdraw consent, subject will be weaned off study drug. If the subject awakens, he/she will be informed of their participation in the study and that their records were reviewed. Banking of blood for genetic studies requires a separate informed consent. The genetic sample will not be drawn until consent for the procedure has been obtained. In the event that an LAR is identified but is unable/unwilling to come into the hospital for an in-person discussion, we are requesting the option to have a physician investigator discuss the study and go through the consent over the phone. We would then email a copy of the consent to the LAR and request that he/she respond that they are agreeable for the patient to participate in the genomic

portion of the trial, or indicate that they are not agreeable. We will have two people independent of the study, usually clinical nurses or physicians, witness the process. We would then draft a Note to File to keep in the subject's study folder outlining exactly what happened, along with a copy of the entire email discussion.

In the event that the LAR is unable/unwilling to come into the hospital and does not have access to email, we are requesting a waiver to document written informed consent for the notification of study enrollment only. The physician investigator will discuss the study and will obtain permission for continued participation. A Note to File will be placed in the subject's record documenting the discussion and the LAR's response.

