6.4.6 Adverse Events Reporting Timeline

All SUAE associated with the use of the study drug (ie in the setting of MetHb $> 10\%$ or discovered to be drug associated after unblinding by the safety monitor and considered potentially resulting from the study drug by the DSMB) will be reported to the IRB within 24 hours of discovery of the incident with subsequent follow-up submission of a detailed written report.

The FDA will be notified by telephone or facsimile transmission of a human SUAE no later than 7 calendar days after receiving the respective human adverse event information, followed by the

subsequent submission of a written IND Safety Report.

Serious and unexpected adverse events associated with the use of the study drug or procedures will be reported to the IRB with subsequent follow-up submission of a detailed written report in accordance with the respective policies and procedures of the IRB. Written IND Safety Reports will be submitted to the FDA as soon as possible and, in no event, later than 15 calendar days following the investigator-sponsor's receipt of the respective adverse event information.

A summary report of the findings will be prepared and submitted to the regulatory agencies.

6.4.7 Withdrawal of Subjects and Stopping Criteria:

Subjects withdrawn from the study due to concern for SAE will be followed for all clinical outcomes but no further lab or imaging data will be collected. These subjects will not be replaced within the study. Subjects will not be withdrawn after enrollment except if requested by the subject or surrogate after notification. In this event all data and specimens required for study outcomes obtained up to that time and clinical outcomes to DC will be retained.

Discontinuation of the Clinical Trial:

This study can be stopped only by the DSMB. In such a case we will complete collection of clinical outcomes in all enrolled subjects (up to 90 d after OHCA). Subjects will not be notified of early study termination.

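### With no imputation, day-30 and day-90 tests would drop almost only discharged survivors: survival is understated, and other outcomes and the iNO comparison can be biased either way

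*Combined protocol and SAP*

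**What the plan says.** Section 2.5.5 reasons from the primary endpoint, which is ascertained at discharge: "we expect no missing data though all analyses will be performed assuming a missing at random mechanism". It continues: "No data imputation will be performed though standard sensitivity analyses, using standard missing data techniques may be used". The sensitivity analyses are optional and unnamed.

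The secondary endpoints in section 2.4 reach well past discharge. One is "Survival to hospital discharge, 30 and 90 days after initial OHCA"; favorable CPC, favorable mRS and favorable location are defined at the same later times. Section 2.2 schedules these outcomes at discharge "and for follow up at day 30 (+/- 3 days) and day 90 (+/- 3 days) after OHCA". It describes their collection as follows: "Follow-up data that will be obtained will not require a subsequent visit, but rather just a phone call". Later in the same section, record review comes first, with in-person or telephone contact for whatever the records lack. Survival, CPC, mRS, NYHA class and location are starred, meaning that no missing values are expected.

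Section 6.4.7 separates two kinds of withdrawal. Subjects withdrawn over a safety concern are still followed for clinical outcomes. If the subject or surrogate asks to withdraw, "all data and specimens required for study outcomes obtained up to that time and clinical outcomes to DC will be retained", and nothing later is promised. Section 5.2 makes such a request possible both for surrogates and for recovering subjects: "If the subject awakens, he/she will be informed of their participation in the study".

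On the test, section 2.5.2 states: "Other secondary dichotomous outcomes will be summarized and compared by chi squared tests", with exact methods for small samples. It also lists generalized linear mixed models for comparisons over several times, and Kaplan-Meier with log-rank tests for time-to-event endpoints. It assigns neither to the day-30 and day-90 outcomes.

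**The concern.** The reason given for needing no missing-data method holds for the discharge composite and for nothing later. After discharge, the pattern of missing values is not neutral. A subject who died in hospital has a known day-90 result on survival, and counts as a failure on CPC 1-2, mRS 0-3 and favorable location. A subject discharged alive has a known result only if the records or a contact supply it, and none need be kept after a requested withdrawal. Whether a value can be missing therefore depends on survival to discharge.

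That dependence is on something the trial records, so a missing-at-random analysis that uses discharge status could deal with it. A two-by-two chi-squared test on observed values does not use discharge status. Each lost survivor leaves the denominator while every in-hospital death stays in.

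Section 2.5.3 treats improvement in any secondary clinical outcome as preliminary evidence of efficacy that would call for a larger trial. Bias in these outcomes could therefore affect the decision to run that trial.

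**Working it through.** **The plan's own figures.** The documents give no figure for loss at day 30 or day 90. The nearest is the dropout allowance in section 2.5.1: 60 per arm raised to 65 for 5% dropout. 60/0.95 = 63.2, so 64 would do and 65 is consistent. Reading the 23% reduction as absolute, with two-sided alpha 0.05, 60 per arm gives power of 78.1%, 80.1% and 82.3% at control rates of 80%, 82.5% and 85%. The design figure is reproduced.

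**Inputs.** From the documents: 65 per arm; 5% planned dropout; under 1% experienced (section 2.5.1); 70-80% expected mortality (section 6.4.5), so 20-30% alive. Assumed: 25% true survival on placebo and 45% on iNO, the loss fractions, and the condition of those lost.

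**Formula.** Let p be the true success rate among all randomised, k the share of the arm that is missing, and r the success rate among the missing. Then

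available-case rate = (p − k·r)/(1 − k).

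This is below p exactly when r > p. If all the missing are survivors, r = 1 for survival.

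**1. Planned dropout, same head count in each arm, all survivors.** 5% of 65 = 3.25 lost per arm.
- Placebo: 16.25 survivors (0.25 × 65); (16.25 − 3.25)/(65 − 3.25) = 13/61.75 = 21.1%.
- iNO: 29.25 survivors (0.45 × 65); (29.25 − 3.25)/61.75 = 26/61.75 = 42.1%.
- The risk difference goes from 20 to 21.1 points and the odds ratio from 2.45 to 2.73. Equal head counts are unequal fractions of survivors (3.25/16.25 = 20% against 3.25/29.25 = 11%), so here the apparent benefit grows.
- At 1% of each arm (0.65 subjects): 15.6/64.35 = 24.2% and 28.6/64.35 = 44.4%, a difference of 20.2 points.

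**2. Same loss fraction among those discharged alive.** Assume 25% and 45% discharged alive, 95% of them alive at day 90, and loss fraction m unrelated to outcome among them. Then p = 0.95d, k = d·m and r = 0.95, where d is the share discharged alive.

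| m | placebo | iNO | difference (points) | odds ratio |
|---|---|---|---|---|
| 0 (truth) | 23.8% | 42.8% | 19.0 | 2.397 |
| 5% | 22.8% | 41.5% | 18.7 | 2.400 |
| 10% | 21.9% | 40.3% | 18.4 | 2.403 |
| 20% | 20.0% | 37.6% | 17.6 | 2.408 |

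The rates fall, the difference shrinks slightly and the odds ratio hardly moves.

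**3. Different loss fractions, same assumptions.**
- 5% of placebo and 20% of iNO survivors lost: difference 14.7 points, odds ratio 2.03.
- 20% of placebo and 5% of iNO survivors lost: difference 21.5 points, odds ratio 2.84.
- No true effect, 30% discharged alive in both arms: the same two pairs give odds ratios of 0.85 and 1.18.

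**4. CPC, mRS and location.** Take 45% discharged alive and 60% of them in good condition, so p = 27%. With 20% of them lost, k = 0.45 × 0.20 = 0.09.
- r = 0.60 (the lost resemble the others): (0.27 − 0.054)/0.91 = 23.7%.
- r = 0.10: (0.27 − 0.009)/0.91 = 28.7%.
- r = 0: 0.27/0.91 = 29.7%.

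The sign of the bias depends on how the lost survivors fare.

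**5. Bounds.** In the m = 10% row of step 2, 2.5% and 4.5% of the arms are missing, and 21.4% and 38.5% of each arm are observed alive. Worst case for iNO: 38.475 − (21.375 + 2.5) = 14.6 points. Best case: (38.475 + 4.5) − 21.375 = 21.6 points.

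**The case against.** The strongest reply is that little will be missing and that the plan already lists suitable tools. The outcomes are starred, records are searched before anyone is telephoned, safety withdrawals stay in follow-up, and experienced dropout is under 1%. A mixed model over discharge, day 30 and day 90 would use discharge status without imputation, and Kaplan-Meier would censor rather than drop. Section 2.5.5 permits sensitivity analyses, and section 2.2 mentions an a priori analysis plan for missing data. The trial is double blind, so there is no evident reason for unequal loss.

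Much of this limits the size, and it makes dropping missing cases an inference rather than stated text. It does not close the gap. The star expresses an expectation, while section 6.4.7 can create missing values by rule. The dropout figures support power for a discharge endpoint, not 90-day contact. The mixed model and Kaplan-Meier are not assigned to these endpoints, and the chi-squared sentence is the one that fits them. The remark about an a priori plan concerns secondary mechanistic data, and section 2.5 is the only analysis text supplied.

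There is also an exception to the pattern. Section 6.5.1 lets a withdrawing subject or representative ask for study data to be destroyed, which could remove in-hospital deaths too. That has to be reconciled with section 6.4.7.

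A reader might infer that every day-30 and day-90 rate is biased down and that a true benefit must shrink. The documents do not support that. The subjects lost may include impaired ones withdrawn by a surrogate, which can push CPC, mRS and location upward (step 4). The effect on the comparison depends on the scale and on loss by arm (steps 1 to 3).

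**Conclusion.** The gap stands, for secondary outcomes only; the primary composite is unaffected. If the chi-squared sentence is applied to observed values, understatement of day-30 and day-90 survival is close to certain, because the lost survivors would have to do worse than the whole randomised group, deaths included, to reverse it. For CPC, mRS and location the direction is open. The iNO comparison can move either way, mainly when the fraction of survivors lost differs by arm.

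The size is modest at the plan's own dropout: about 4 points on placebo and 3 on iNO if 5% of each arm is lost and all are survivors, and under 1 point per arm at 1%. One could build alarming cases. Losing 10% of placebo and 30% of iNO survivors cuts a true 25% versus 45% to 23.1% versus 36.4%, a difference of 13.3 points. That needs about 9 iNO subjects lost (0.30 × 29.25 = 8.8, or 13.5% of the arm) against fewer than 2 on placebo, and nothing in the documents predicts it. All survival and loss rates here are assumptions, apart from the expected mortality and dropout figures.

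**What to change.** Rewrite section 2.5.5 as follows:
- Limit the ban on imputation to the discharge composite.
- Keep all randomised subjects in the day-30 and day-90 analyses, with in-hospital deaths counted as known outcomes.
- Analyse survival by the Kaplan-Meier and log-rank methods already listed, censoring at the date last known alive.
- For CPC, mRS and location, use either a simple imputation or the mixed model already listed, based on arm and discharge status. With so few survivors the model should stay small.
- Require best-case and worst-case bounds, and report the number missing by arm and by discharge status.
- Reconcile section 6.4.7 with section 6.5.1 on what is kept after a withdrawal.

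The cost is wording and a little analysis, with no new data. The downside is a modelling assumption for a few subjects, including that censored survivors resemble those still followed. The bounds show how much depends on it.

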2.5.6 Data Management

Subjects will be assigned a study ID upon entry and all data/samples stored using that ID. Linkage to patient identifiers will be maintained in a secure spreadsheet and will include name, DOB and MRN. De-identified clinical and lab data will all be stored in a web based database to be maintained by [name] research assistant who has prior experience from other studies. All data will be stored and managed with adherence to all relevant laws and HIPAA guidelines to ensure the safety and privacy of patient data.

3. HUMAN SUBJECTS

3.1 SUBJECT POPULATION

3.1.1 Inclusion of Women and Minorities

Women and Minorities will be included in the subject population

3.1.2 Inclusion of Children

Children will not be included in the subject population

3.1.3 Inclusion of Prisoners

Prisoners will not be included in the subject population

3.2 INCLUSION CRITERIA

Inclusion criteria do not change any subgroups.

Intubated and comatose adult (>18 yo)

Out-of-hospital cardiac arrest (OHCA)

Cardiac arrest within an emergency department or outpatient medical center will be included.

OHCA includes EMS witnessed cardiac arrest.

ROSC within 40 min of CPR initiation

FOUR Brainstem score ≥ 2

Patient must have pupil OR corneal reflex before enrollment

3.3 EXCLUSION CRITERIA

Exclusion criteria do not change any subgroups.

- Traumatic etiology of OHCA
- Prisoner
- Known pregnancy
 - o B-HCG screening is NOT REQUIRED for enrollment in women of appropriate age
- Hemodynamic instability defined as:
 - o > 1 recurrent arrest prior to enrollment
 - o Inability to maintain mean arterial blood pressure (MAP) > 65 using vasopressors and inotropes (ie actively up titrating medications or giving fluid bolus)
- Cerebral edema defined as:

- Head CT grey-white ratio < 1.2
 - Fixed and dilated pupils without another explanation
- Malignant EEG upon presentation (not required as screening) defined as:
 - Myoclonic status epilepticus
 - Non-convulsive status epilepticus
 - Generalized periodic epileptiform discharges
- ROSC >3h from time of ED arrival (Treatment allocation must be within 4h so anything that will prevent this is reason for exclusion)
- Alert and interactive patient with minimal evidence of neurologic injury
- Plan to extubate within 12 hours
- PCAS opinion that patient will die with >95% likelihood. This may be based on:
 - Multiple medical comorbidities
 - Late discovery of DNR or advanced directive
 - Terminal diagnosis (other than OHCA; may have caused OHCA)
 - Clinical judgement based on current exam and data
- Known intracranial hemorrhage or acute cerebral infarction; Head CT is NOT REQUIRED prior to enrollment
- Patient is known to be taking PDE5 inhibitors, sGC stimulator, or has a known diagnosis of Chronic thromboembolic pulmonary hypertension (CTEPH), pulmonary hypertension (PAH), or erectile dysfunction
- Known enrollment in another acute interventional trial

